7.0 Side effects

At every visit study personnel will enquire about adverse effects in a standardized manner, though there is no intervention other than diet. In the event of a positive response, the adverse effect will be assessed by the investigator and the likelihood of a causal relationship with HS/LS diets (definitely, probably, uncertain, probably not, definitely not) and regarding its severity (mild, moderate, severe). Patients who develop serious adverse events causally related to participation in the study will be discontinued from the study.

- a. **Side effects of salt supplements and study procedures:** Salt is a naturally occurring compound found in most food products. No side effects have been reported from salt intake, however salt could cause nausea. The amounts being administered for the study will be within safe levels determined from previous similar studies and the general population intake. A high-salt diet may increase blood pressure in some people. We will provide patients with a home blood pressure monitor so that they can take their blood pressure at home once a week and ask them to call us if it is greater than 160/100 mm Hg. Venipuncture may cause bleeding or bruising. The automatic inflation of the arm cuff for ambulatory blood pressure monitoring could disturb sleep. MRI: There are no known major

risks with an MRI scan; but, it is possible that harmful effects could be found in the future. Even though the tunnel is open, it may bother some patients (claustrophobia), and they hear the noise made by the magnet during the scan. We provide earplugs to reduce the noise. Metal pieces in the body could move during the scan and damage nearby tissues or organs. Patients will not be able to have this scan if they have a non-MRI safe device implanted such as an aneurysm clip in the brain, a heart pacemaker or defibrillator or a cochlear implant. They also may not be able to have this scan if they have iron-based tattoos or pieces of metal (bullet, BB, shrapnel) close to or in an important organ (such as the eye). We will exclude pregnancy by performing a urine test prior to the MRI. Certain metal objects like watches, credit cards, hairpins, writing pens, etc. may be damaged by the machine or may be pulled away from the body during the scan. For these reasons, patients are asked to remove these objects before going into the room for the scan.

b. Reporting of adverse events and noncompliance: Serious adverse events (SAEs) will be reported to the Vanderbilt Institutional Review Board within 10 days of the PI's notification of the event.

An SAE is an adverse event that meets any of the following criteria:

1. Results in death.
2. Is life threatening. This definition implies that the subjects, in the view of the investigators, are at immediate risk of death from the event as it occurred. It does not include an event that, had it occurred in a more severe form, might have caused death.
3. Requires inpatient hospitalization or prolongs existing hospitalization. (Hospitalization for surgeries planned before study entry will not be considered SAEs)
4. Results in persistent or significant disability and /or incapacity.
5. Results in a congenital anomaly or birth defect. This criterion applies if a congenital anomaly/birth defect is diagnosed in a child of a subject who participated in this study and received study drug.
6. Other important medical events. Judgment should determine whether an adverse event should be classified as serious in other situations, such as important medical events that may not be immediately life threatening or result in death or hospitalization but may jeopardize the subject or require intervention to prevent one of the outcomes listed above. Examples of such events are allergic bronchospasm requiring intensive treatment in an emergency room or at home, convulsions that do not result in inpatient hospitalization.

Non-serious adverse events and instances of non-compliance with the protocol will be submitted at the time of annual review. The progress of the study will be monitored in an ongoing fashion by the PI at weekly lab meetings. There are no plans for a DSMB

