High salt intake adversely affects blood pressure, endothelial function, insulin resistance, and inflammation. The negative impact of high dietary salt intake on blood pressure and thus cardiovascular outcomes such as stroke, coronary artery disease, and heart failure is well documented (<http://www.cdc.gov/salt/>). In addition to increased blood pressure, high salt intake or the predisposition to increase blood pressure with salt (salt sensitivity) is associated with endothelial dysfunction^{7,8}, insulin resistance^{9,10}, vascular stiffness¹¹, and increased levels of markers of inflammation¹² - all present in RA. Restriction of dietary sodium clearly improves blood pressure and improves endothelial dysfunction in the general population^{8,13,14}, with less clear effects on insulin resistance and markers of inflammation. Despite the increased prevalence of hypertension in RA, the effect of reducing salt intake on blood pressure and other cardiovascular risk markers in RA is not known.

In addition, high salt intake may adversely affect autoimmune inflammatory disease and vascular health. Recently, new findings implicate high sodium intake as being pro-inflammatory and important in the pathogenesis of autoimmune inflammatory disease¹⁵. High salt intake induced the formation of TH-17 cells (that produce interleukin (IL)-17) and exacerbated inflammation in experimental autoimmune encephalitis - a well-established animal model of autoimmunity¹⁵. TH-17 cells and their product, IL-17, are critical to the pathogenesis of RA¹⁶ and the maintenance of inflammation in patients who respond incompletely to disease modifying therapy¹⁷. Moreover, TH-17 cells and IL-17 promote hypertension and vascular dysfunction¹⁸. Thus, decreasing salt intake in RA could decrease not only cardiovascular risk markers but also IL-17- mediated inflammation. However, the effect of modifying salt intake on inflammation and vascular responses in RA is not known.

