The order of high-sodium (HS) or low-sodium (LS) diets will be randomized. Patients will be randomly assigned to be on the high-sodium diet (200mmol/24hours x 8weeks) or low-sodium diet (50mmol/24hours x 8 weeks) with crossover separated by 4-week washout period. We will allow a 7-day window on the diet (i.e., to facilitate scheduling the diet can be between 7-9 weeks), and we will allow a 1-week window for the washout

(i.e., washout can be 3-5 weeks). Subjects will choose a rotation of low-sodium meals from a predetermined list from a commercial vendor (Mom's Meals) that will be used to provide 2 meals (lunch and dinner)/day that the vendor will deliver at approximately 7 day intervals. If there is disruption in shipping the meals, the dieticians will direct the participants on which foods to purchase to continue the diet without interruption. Participants will be reimbursed for needed diet purchases upon submission of receipts.

Staff of the Vanderbilt Diet, Body Composition, and Human Metabolism Core (under the supervision of [name]) determine breakfast and snacks appropriate for the HS and LS diets and provide instructions to subjects. These Na^+ intake levels are in the range of high current intake estimates (~12 g/d) and AHA recommendations (~4 g/day). HS and LS phase menus will be standardized for potassium and calorie composition and will be similar in the HS and LS phases except for the addition of table salt and salty snacks during the HS phase. Treatment order will be randomized with each diet treatment for a period of 8 weeks and a 4-week wash-out period between treatments. To facilitate diet conformity we will provide patients with salt packets and high-salt snacks or drinks, and we will also purchase and provide a supply of a low-sodium breakfast for patients (e.g., a selected breakfast cereal). These items will be curbside pickup for participants on Visit 1 and 3 from the Metabolism Core. Study personnel will communicate with patients at approximately 1-2 week intervals during the HS and LS diets to provide nutrition counseling, resolve problems, optimize diet adherence, and coordinate visits. If patients feel hungry or lose weight on the prepared meals, study dietitians will provide patients with a list of allowable supplementary dietary items that patients can prepare at home and add to the prepared meals and snacks provided. During the washout period (weeks 9-12) subjects will resume their habitual diet.

Schematic of Crossover Design

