6.0 Study Procedures

a. Screening

Patients with RA who fulfill inclusion and exclusion criteria will be offered the opportunity to discuss the study with a member of the study team by telephone or video conferencing. If they agree to participate in the study, they will indicate the same by signing a copy of the informed consent document, either electronic or paper. Consented subjects will then be screened for participation in the study.

If participants meet criteria to continue during the virtual screening, they will be scheduled for an in-person screening at the VUMC Clinical Research Center. A kit will be mailed to participants before the in-person screening which will include a face mask to be worn by the participant when they come to VUMC. Patients will speak by telephone with the CORE dietitian for assessment of dietary intake,

selection of meals to be delivered, and diet instructions. Then, enrolled patients will be seen at baseline (study visit 1, week 0 - randomization) and then at visits 2 (week 8), 3 (end of washout week 12), and 4 (week 20) (See Schematic).

b. Baseline Data Collection

Screening will be divided into two parts: a virtual screening and an in-person screening. During the virtual screening, clinical details, including self-reported height, weight, joint count, current and past smoking history, menopausal status, duration of menopause, family history of cardiovascular disease, and current and past estrogen replacement history will be obtained. Cumulative medication history and cardiovascular therapies will be obtained from the patient and the medical record. Participants will complete an online health assessment questionnaire at baseline and at each visit.

Participants will be called no earlier than 72 hours in advance of their visit and no later than 12 hours prior to their visit to answer questions on COVID-19 exposure and symptoms per VUMC CRC protocol.

When participants arrive at VUMC wearing their face masks, they will have their temperature checked and will be asked about COVID-19 symptoms before they can enter the CRC.

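### Section 7.0a says no side effects of salt have been reported, against the plan's own text, and omits possible RA worsening; separately, no symptom question is specified between visits

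*Combined protocol and SAP*

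**What the plan says.** On risk, Section 7.0a states: "No side effects have been reported from salt intake, however salt could cause nausea". It then says that the amounts used are within safe levels judged from similar studies and from general population intake. Two sentences after the quoted one it accepts that a high-salt diet may raise blood pressure in some people. It provides a home monitor for weekly readings and asks participants to call if a reading exceeds 160/100 mm Hg.

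Section 1.0 takes a different line: "High salt intake adversely affects blood pressure, endothelial function, insulin resistance, and inflammation". It calls the effect on blood pressure, and through it on cardiovascular outcomes, well documented. On RA it is more cautious: "high salt intake may adversely affect autoimmune inflammatory disease and vascular health". Hypothesis 1 in Section 3.0 is that less dietary sodium will reduce inflammation in RA.

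On ascertainment, Section 7.0 says: "At every visit study personnel will enquire about adverse effects in a standardized manner". Section 6.0a places visits 1 to 4 at weeks 0, 8, 12 and 20. Section 5.0f allows each diet to run 7 to 9 weeks, and the "washout can be 3-5 weeks".

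Between visits, Section 5.0f says: "Study personnel will communicate with patients at approximately 1-2 week intervals during the HS and LS diets". The stated purposes are dietary advice, sorting out problems, adherence and visit scheduling. Section 8.0 adds a dietary history to assess compliance. Neither section mentions adverse effects or joints.

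**The concern.** There are two separate matters.

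The first is wording. A risk section should agree with the rationale of its own trial. Here the general statement about salt intake denies what the background asserts as fact. The one disease-specific risk that the trial is built around, worsening of RA on the high-salt diet, is not listed. For the low-salt diet no anticipated effect is listed, although Section 7.0 asks the investigator to judge causality for both diets, and Section 5.0f already foresees hunger or weight loss on the prepared meals.

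The second is a gap in ascertainment. If adverse effects are asked about only at visits, a flare or other symptom that begins and settles within a diet phase is captured at the time only if the patient volunteers it. Patients know their diet (Section 4.0), so what they volunteer could differ between diets. A fixed question put in the same words in both phases would reduce that and would help to date each event to a diet.

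**Working it through.** **1. The statements side by side.**

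| Place | Content | Relation to the quoted sentence in 7.0a |
|---|---|---|
| 1.0 | High salt harms blood pressure, endothelium, insulin resistance and inflammation; stated as fact | Direct conflict |
| 7.0a, two sentences later | High-salt diet may raise blood pressure in some people | Conflict within one paragraph |
| 1.0 | High salt may worsen autoimmune inflammatory disease; the effect of changing salt intake on inflammation in RA is not known | Not a conflict with the word reported; a hypothesised risk missing from the list |
| 3.0, Hypothesis 1 | Less sodium reduces inflammation in RA | Same: omission |
| 5.0f | Hunger or weight loss may occur on the prepared meals | Foreseen there, absent from 7.0 |

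**2. Timing of the standardised enquiry.** The inputs are the visit weeks 0, 8, 12 and 20 (6.0a) and the windows in 5.0f.

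- Nominal gaps: 8 − 0 = 8 weeks, 12 − 8 = 4 weeks, 20 − 12 = 8 weeks.
- Diet window: 8 ± 1 = 7 to 9 weeks, which reproduces the range stated in the plan. Washout window: 4 ± 1 = 3 to 5 weeks, also as stated.
- Longest permitted gaps between visits: 9, 5 and 9 weeks.
- The enquiries at weeks 0 and 12 come before a diet starts. Those at weeks 8 and 20 come at the end of one. Hence there is one on-diet enquiry per phase, at its end, 7 to 9 weeks after the diet began.

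**3. What the existing contacts could add.** Assume evenly spaced contacts counted from the start of the diet, with a contact that falls on the end-of-phase visit not counted as extra.

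- Weekly, 8-week phase: 8 / 1 = 8, less 1 at the visit = 7.
- Every two weeks, 8-week phase: 8 / 2 = 4, less 1 at the visit = 3.
- So there would be about 3 to 7 extra enquiries per 8-week phase.
- With a 7-week phase the range is 3 (weeks 2, 4, 6) to 7 − 1 = 6. With a 9-week phase it is 4 (weeks 2, 4, 6, 8) to 9 − 1 = 8.

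**4. What is already covered between visits.** Blood pressure: weekly home readings with a call-in threshold (7.0a). Weight: weekly self-report to staff (6.0c). RA flare: Section 5.0e says what follows if a flare needs a significant change in therapy, but no scheduled question between visits is specified that would find one. Other symptoms: none specified.

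**The case against.** The case on the other side is substantial, and much of it stands.

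- The paragraph is about salt supplements and procedures, and can be read as a remark on tolerability. It does go on to disclose the blood pressure risk. A reader who stopped at the quoted sentence might infer that this risk is undisclosed or unmonitored. It is not: it is stated two sentences later and followed by weekly home readings, and ambulatory monitoring is done at all visits (6.0c).
- RA activity is not ignored. DAS28 with joint examination is done at each visit, a health questionnaire is completed at each visit, and flares needing a significant change in therapy are addressed in 5.0e.
- The visit interval contradicts nothing in the plan. Enquiry at visits is a design choice, and it is the same in both diet phases.
- The stated purpose of resolving problems does not exclude symptoms, so the 1-2 weekly contacts may already bring some to light.
- It is tempting to add that events will be under-reported, or that the comparison of safety between diets is unreliable. The documents give no source for the first, and Section 12.0 plans no such comparison.
- It would also go too far to say that the trial expects the high-salt diet to harm patients with RA. Section 1.0 says may and not known, and Sections 5.0f and 7.0a place the intakes within current population and recommended ranges. Oedema appears only as an exclusion criterion, not as an expected effect.
- The absence of a DSMB does not mean an absence of oversight: Section 7.0b provides for weekly review by the principal investigator.

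Three things remain after this: the sentence conflicts with Section 1.0 and with its own paragraph, RA worsening is not named in Section 7.0, and a structured enquiry is specified only at visits.

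**Conclusion.** The point holds as a minor one, in two parts. The quoted sentence in 7.0a cannot stand beside Section 1.0 and the later blood pressure sentence, and the risk section leaves out the hypothesised risk to RA. Separately, structured enquiry gives one on-diet time point per phase, up to 9 weeks after the diet starts, although contacts every 1-2 weeks already take place and could carry a question.

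No sample size, power figure or planned estimate is affected. The gain lies in a consistent risk section, earlier notice of symptoms, and better dating of events to a diet. The count of 3 to 7 extra enquiries assumes evenly spaced contacts in an 8-week phase. The conclusion about enquiry assumes that the contacts have no adverse-effect question beyond what Sections 5.0f and 8.0 describe; if a call script already has one, only the wording needs attention. The consent form is not in the text reviewed, so nothing is concluded about what participants are told.

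**What to change.** 1. In 7.0a, reconcile the quoted sentence with Section 1.0 and with the blood pressure sentence in the same paragraph.
2. In 7.0, name possible worsening of RA on the high-salt diet as a hypothesised risk, and refer to the hunger or weight loss on prepared meals already foreseen in 5.0f.
3. In 5.0f and 8.0, add one fixed adverse-effect and joint-flare question to the existing 1-2 weekly contacts, in identical words in both diet phases, with the onset date recorded. The dietitian knows the diet (4.0), so the answers should not be passed to the blinded assessors.
4. In 12.0, add a descriptive table of adverse effects and flares by diet at onset, with washout shown separately.

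How any event is managed stays with the investigator; none of this sets a threshold or a treatment rule. The cost is a wording amendment, a few lines in a contact script, one table, and a few minutes per contact. No visit, procedure or staff is added.

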8.0 Adherence

Study personnel will be in contact with patients every 1-2 weeks and will assess compliance by dietary history taking.

9.0 Anticipated Results

No previous studies of this nature have been done in RA. We anticipate that low dietary sodium may reduce blood pressure, vascular stiffness, endothelial dysfunction, insulin resistance, tissue Na^+ levels, and inflammation in patients with RA.

10.0 Statistical Methods

a. Sample Size

We will plan to enroll 50 RA patients assuming that many will drop out. The sample size estimation of n=18 was based on two outcomes of major interest: the comparison of the change from baseline for 1) DAS 28 and 2) Skin Na⁺ concentrations using a paired t-test comparing post-treatment values after receiving HS or LS diet. However, in the actual data analysis, we will compare the change from baseline to post-treatment value between the two treatment phases (i.e., linear mixed effect models) which will improve power, thus the sample size analyses presented is the most conservative. Sample size was estimated using PS-Power for a paired t-test with a 2-sided test at a significance level of 5%. Assuming that less than 20% of subjects will dropout or have incomplete data is a reasonable assumption based on our previous studies. If the number of dropouts exceeds our estimate we will replace them. For patients who are withdrawn or lost to follow-up without data for week 8 for either arm, an intention-to-treat approach will be applied. For inflammation (DAS28 score) a sample size of 18 patients will provide 95% power to detect a difference between HS and LS arms of 1.0 unit – a clinically meaningful reduction. For Skin Na⁺ measurements the standard deviation (SD) is approximately 5.0 mmol/L and a difference between groups of this magnitude represents a clinically important difference. A sample size of 18 patients will provide ~98% power to detect a difference in skin Na⁺ of 5 mmol/L, respectively. For secondary outcomes measures (e.g., inflammation (e.g., CRP, IL-6, T cell populations) and vascular function (e.g., 24 h BP) we have >95% power to detect a difference between groups equivalent to 1 SD – a difference likely to clinically relevant.

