4.0 General Approach

Our approach will be to gather data on vascular (including blood pressure, augmentation index, vascular stiffness, endothelial function), inflammation (including DAS28, IL-17, IL-6, TNF- α), metabolic (including insulin, glucose, catecholamines), microbiome (stool and saliva), oxidative stress (F2 isoprostanes excretion), and tissue Na^+ measures after, a high-salt and low-salt intake each administered for 8 weeks, in random order, in a crossover study with a 4-week washout period between high-salt and low-salt diets in 22 patients with moderately active RA. It is not possible to blind patients to diet - thus patients and the dietitian will know whether a diet is high-salt (HS) or low-salt (LS). However, we will ensure that investigators performing assessments are blind to the dietary intervention.

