11.0 Early Withdrawals and Dropouts

Intention-to-treat analysis, which focuses on all randomized patients with at least one follow-up evaluation, will be used as this has been the standard approach used by many researchers and regulatory agencies. For either, or both HS and LS treatment phases of this crossover trial, when a patient drops out without having any follow-up data assessed, data points for the patient will be excluded from the analysis. Due to the nature of the pilot study with a relatively small population, we expect that virtually all patients enrolled in the study will return for a follow-up visit, thus the number of dropouts is likely to be far less than ~20% which we built into our samples size by consenting 22 patients with goal of having at least 18 subjects' data for both treatment phases. Dropouts will be defined as patients who are randomized but never return (i.e., there is no follow-up visits).

Possible confounding could occur when a patient is included in the analysis of phase 1 and excluded from phase II due to dropout. We will re-assess baseline balance between patients who are excluded in phase I and in phase II on demographic or clinical characteristics of patients to examine potential confounding by dropouts. For patients who are withdrawn or lost to follow-up after being randomized, the last visit after baseline screen will be used to replace missing values (last observation carried forward, LOCF method). ANCOVA with LOCF method will be used to analyze the data as a more conservative approach. Exploratory analyses will also be performed by examining the findings in the subset of subjects who are adherent to the diet (\pm 20% of target Na intake).

If the participant at any time requests to withdraw from the study, he or she may do so. We will continue to store and use samples and information obtained before withdrawal unless the participant notifies the principal investigator in writing with a date of notice. In the event of withdrawal from the study, no additional collection of information from the date of withdrawal will be performed. We will enquire from participants who withdraw whether they may be contacted for future studies.

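### The planned enrolment of 50 contradicts the under-20% loss assumption in the same paragraph and the 22 patients in Sections 4 and 11

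*Combined protocol and SAP*

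**What the plan says.** Section 10.0, a. Sample Size, opens with the enrolment figure: "We will plan to enroll 50 RA patients assuming that many will drop out". It then bases the calculation on 18 patients. Further down the same paragraph it gives the loss assumption: "Assuming that less than 20% of subjects will dropout or have incomplete data is a reasonable assumption based on our previous studies". It adds a replacement rule with no maximum: "If the number of dropouts exceeds our estimate we will replace them".

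Section 4.0 describes the crossover "between high-salt and low-salt diets in 22 patients with moderately active RA".

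Section 11.0 expects nearly everyone to return and says that "the number of dropouts is likely to be far less than ~20% which we built into our samples size by consenting 22 patients". The purpose it gives for that number is a two-phase target of 18 patients. It then fixes the term: "Dropouts will be defined as patients who are randomized but never return". Its next paragraph nevertheless uses the word for a patient who is "included in the analysis of phase 1 and excluded from phase II due to dropout".

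**The concern.** The plan holds two incompatible expectations about attrition. One is that many patients will be lost, so 50 are needed. The other is that fewer than 20%, and probably far fewer, will be lost, so 22 are enough. The two enrolment figures differ more than twofold, and no stated rate leads to the larger one.

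Three practical matters depend on which is meant:

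- **End of recruitment.** It could be 22, 22 plus an unlimited number of replacements, or 50.
- **Start of replacement.** Replacement begins when losses exceed the estimate, but the estimate is either under 20% or an unquantified large share.
- **Extent of missing data.** Section 11.0 excludes patients with no follow-up and carries the last observation forward for those withdrawn or lost. These rules are a minor matter at 18% loss and a major one at 64%.

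The shifting use of the word dropout adds to this. The allowance protects a goal of data in both phases. A patient lost after phase 1 defeats that goal but is not a dropout under the Section 11.0 definition.

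**Working it through.** **Inputs.** Section 10.0: n = 18 evaluable; enrolment 50; loss or incomplete data under 20%; paired t-test, two-sided 5%; skin sodium SD about 5.0 mmol/L, difference 5 mmol/L, power about 98%. Sections 4.0 and 11.0: 22 patients.

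**1. Does 18 reproduce?** Take 5.0 mmol/L as the SD of the within-patient difference, which is an assumption because the plan gives it only for skin sodium measurements. Noncentral-t power for a 1-SD difference with n = 18 is then 97.9%, which matches the stated figure of about 98%. DAS28 power cannot be checked because no DAS28 SD is given.

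**2. Does 22 follow from 18 and 20%?**

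- Dividing by the completion rate: 18 / (1 − 0.20) = 22.5, rounded up to 23.
- Multiplying up: 18 × 1.20 = 21.6, rounded up to 22.
- In reverse: 1 − 18/22 = 18.2% loss, which is under 20%.

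So 18, 22 and under 20% belong together.

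**3. Does 50 follow from any stated rate?**

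- Loss needed to go from 50 to 18: 1 − 18/50 = 64%.
- Loss needed to go from 50 to 22: 1 − 22/50 = 56%.
- Completers from 50 at the stated ceiling: 50 × 0.80 = 40.

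Applying n/(1 − d) to 18 gives 24, 30, 36 and 45 at losses of 25%, 40%, 50% and 60%, and reaches 50 only at 64%. None of these rates is in the plan.

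**4. What would 50 mean in practice?** The plan puts no figure on the expected loss, so a range is assumed:

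| Assumed loss from 50 | Two-phase completers | Non-completers | Skin sodium power (same SD assumption) |
|---|---|---|---|
| 20% | 40 | 10 | >99.9% |
| 40% | 30 | 20 | >99.9% |
| 50% | 25 | 25 | 99.8% |
| 64% | 18 | 32 | 97.9% |

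Under the 22-patient version, 22 − 18 = 4 non-completers. The ratio of the two enrolment figures is 50/22 = 2.27.

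**5. When would replacement start?** With 22 enrolled, the fourth loss is 4/22 = 18.2% and the fifth is 5/22 = 22.7%. The fifth is therefore the first to exceed 20%. No upper limit on replacements is given, and nothing ties them to the 50.

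**The case against.** The best defence is that 50 is an administrative ceiling that covers screen failures and replacements. Section 6.0 places consent before screening, so enrolling 50 might mean consenting 50. If replacements are included, the 50 would itself be the cap.

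The text does not support this. Section 10.0 attributes the 50 to dropout alone, and no screen-failure rate appears anywhere. Section 6.0 uses the word enrolled for patients seen at the baseline randomisation visit. Reading the 50 as a consented count does not help, because Section 11.0 applies 22 to consenting. The ceiling reading remains possible as an intention, but the plan would have to state it.

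Some of the case against does stand:

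- No calculation behind the 18 is shown to be wrong. This is a conflict between stated numbers, and power is not threatened.
- The exclusion and LOCF rules concern randomised patients. The upper figure of 32 non-completers assumes that all 50 are randomised and only 18 complete, so it illustrates a limit and is not a forecast.
- The Section 10.0 rate already counts incomplete data as well as dropout, which is close to a two-phase non-completion rate. The narrower definition is in Section 11.0.

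**Conclusion.** The concern holds. The 50, and the expectation of heavy dropout that justifies it, cannot stand beside an under-20% loss assumption and a 22-patient design. Keeping 18 from 22 is an 18.2% loss; keeping 18 from 50 is a 64% loss; and 50 at 20% loss gives 40 completers. These are direct arithmetic on the plan's figures. Only the power values rest on an assumption, namely that 5.0 mmol/L is the SD of the paired difference.

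The consequence is an undefined recruitment target and undefined expected attrition. For illustration, the number of patients not completing both phases could be 4 of 22, or anywhere from 10 to 32 of 50. This should be corrected, but it does not undermine the design.

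**What to change.** Use one enrolment number and one expected non-completion rate in Sections 4.0, 10.0 and 11.0.

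- **If 50 stands:** state the loss rate it allows for, any screen failures or replacements it includes, and the expected number of two-phase completers. Remove the under-20% statement in Section 10.0 and the far-below-20% and 22-consented statements in Section 11.0. Change the 22 in Section 4.0.
- **If 22 stands:** delete the 50 and the expectation of heavy dropout. Say whether replacements come on top of the 22, and up to what number.
- **In either case:** count as non-completion any patient missing either end-of-phase visit, so that the rate matches the goal of data for both phases. Use that definition for the replacement rule and throughout Section 11.0.

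The cost is wording in three sections. The correction itself adds no patients, although keeping 50 confirms 28 more than Sections 4.0 and 11.0 describe. The clearer definition may also change when replacement begins, so it should be settled before it is next applied.
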